9.1 Handling of drop-outs or missing data

Unless otherwise specified missing data will not be included in the analysis. LEROS data imputation rules are presented section 17.1. and NH data imputation rules are presented section 17.2)

In order to assess the impact of missing data, sensitivity analysis for the primary and secondary endpoints will be performed.

9.2 Interim analysis and data monitoring

No statistical interim analysis is planned.

SNT-IV-005 Statistical Analysis Plan V1.0 07 June 2021 Confidential

To fulfil the regulatory obligations connected to the European Post Approval Commitment (PAES study), annual study reports are submitted yearly as part of the annual reassessment procedure where only study status and safety are discussed. No study endpoints or efficacy analysis are performed.

9.3 Examination of subgroups

Subgroup analyses will be performed in LEROS ITT population, considering time since symptoms onset in **most** recent affected eye at BL.

These subgroups will be analysed separately for patients ≤1 year and >1 year since symptoms onset in most recent affected eye at BL:

- LHON mtDNA mutations:
 - G11778A
 - G3460A
 - T14484C
 - Any other mutation
- Age at BL:
 - < 18 years;
 - \geq 18 years and < 35 years;
 - $\geq 35 \text{ years}$
- Best VA Blindness Category (BC) at BL:
 - Off-chart: CF, HM, LP or NLP
 - Legally blind: 1.0 ≤ logMAR ≤1.68
 - Non-legally blind: logMAR < 1.0

Confidential

10 Disposition

Patients' disposition will be presented separately for LEROS and Natural History (CRS-1 and CRS-2).

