Proportions of Patients and Eyes in the EAP with CRR from VA Nadir following 6 months and 12 months of treatment

CRR from Nadir	Patients		Eyes		Treatment duration at assessment [months]			
in the Efficacy Population	all	CRR	all	CRR	mean	(SD)	min	max
Patients with 6m assessment available	62	CRR at 6m 19 (30.6%)	124	CRR at 6m 30 (24.2%)	5.8	(1.0)	3.1	8.1
12m assessment available	47	CRR at 12m 17 (36.2%)	94	CRR at 12m 28 (29.8%)	11.6	(1.3)	9.1	13.9
at last observation	69	CRR at last obs. 34 (49.3%)	138	CRR at last obs. 55 (39.9%)	15.4	(9.0)	2.8	36.2

6m assessment : closest to 6 months, values at 3-9 months considered

12m assessment: closest to 12 months, values at 9-15months considered

Source Tables : EAP 01-01, EAP 01-02, EAP 01-03, EAP 02-01, EAP, 02-02, EAP 02-03

Magnitude of Recovery in Eyes in the EAP with CRR from VA Nadir at the 6 month, 12 month or at the last observation

Recovery* from Nadir [logMAR]**	N	mean	SD	median	max	min
at the 6 month vist	15	-0.47	0.31	-0.38	-1.00	-0.14
at the 12 month vist	15	-0.62	0.48	-0.40	-1.40	-0.10
at last observation (mean treat. dur. 20.9 m)	15	-0.93	0.42	-1.08	-1.44	-0.14

^{*}for eyes with CRR from BL where recovery had occured at the 6 months visit and a 12 month visit was available, too

Note, for these 15 eyes the VA at BL was also the VA at Nadir

Furthermore, data from the RHODOS and from the EAP provide evidence that the LHON-causative mutation harboured is prognostic of CRR in VA.

Therefore, secondary objectives of this study are to provide information on the effect of treatment duration on both the proportions of patients presenting with CRR and on the magnitude of any response with increasing treatment time and on the influence of the mutation harboured on CRR rate compared to spontaneous CRR (sCRR) untreated control patients.

The study will also allow the assessment of the safety and tolerability of long-term treatment with idebenone, with particular emphasis on the proportion of patients experiencing elevated Liver Function Tests (LFTs) or changes in blood cell counts.

^{**}off chart set to 1.70 [logMAR]

2 Study Objectives and Endpoints

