2.2.2 Secondary Endpoints

- Components of the primary endpoint:
 - Proportion of eyes with CRR of VA from Baseline at Month 12 compared to matching external natural history control group
 - Proportion of eyes in which Baseline VA better than 1.0 logMAR was maintained at Month 12 compared to matching external natural history control group.
- Proportion of eyes in patients treated with idebenone >1 year after the onset of symptoms with CRR of VA from Baseline or in which Baseline VA better than 1.0 logMAR was maintained at Month 12 compared to external natural history control group, in all patients and classified by mutation
- Proportion of eyes and patients treated with idebenone ≤1 year after the onset of symptoms with CRR of VA from Baseline or in which Baseline visual acuity better than 1.0 logMAR was maintained following 6, 18 and 24 months of treatment with idebenone compared to matching external natural history control group, in all patients and classified by mutation

- Proportion of eyes/patients treated with idebenone ≤1 year or >1 year after the onset of symptoms with "Off-chart" VA at Baseline in whom VA improves to better than 1.60 logMAR by Month 6, 12, 18 and 24
- Proportion of eyes/patients treated with idebenone ≤1 year or >1 year after the onset of symptoms with VA in the categories of better than 1.0 logMAR, 1.0 to 1.68 logMAR and above 1.68 logMAR at each assessment time point up to Month 24
- Safety as assessed by AE count and laboratory analyses during the study

3 Study Design

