4.2 Secondary Endpoints

- Components of the primary endpoint:
 - Proportion of eyes with CRR of VA from BL at Month 12 compared to matching external NH control group
 - Proportion of eyes in which BL VA better than 1.0 logMAR was maintained at Month 12 compared to matching external NH control group
- Proportion of eyes in patients treated with Raxone® >1 year after the onset of symptoms with CRR of VA from BL or in which BL VA better than 1.0 logMAR was maintained at Month 12 compared to external NH control group, in all patients and classified by mutation
- Proportion of eyes and patients treated with Raxone® ≤1 year after the onset of symptoms with CRR of VA from BL or in which BL VA better than 1.0 logMAR was maintained following 6, 18 and 24 months of treatment with Raxone® compared to matching external NH control group, in all patients and classified by mutation
- Proportion of eyes/patients treated with Raxone® ≤1 year or >1 year after the onset of symptoms with "Off-chart" VA at BL in whom VA improves to better than 1.60 logMAR by Month 6, 12, 18 and 24
- Proportion of eyes/patients treated with Raxone® ≤1 year or >1 year after the onset of symptoms with VA in the categories of better than 1.0 logMAR, 1.0 to 1.68 logMAR and above 1.68 logMAR at each assessment time point up to Month 24
- Safety as assessed by AE count and, as available, laboratory analyses during the study.

SNT-IV-005 Statistical Analysis Plan

Study: SNT-IV-005

Confidential

5 Design and type of the study

The Sponsor has been granted an EU marketing authorisation (MA) under exceptional circumstances for Raxone[®] (idebenone 150 mg) for the treatment of visual impairment in adolescent and adult patients with Leber's Hereditary Optic Neuropathy (LHON) in September 2015.

Pursuant to Article 14(8) of Regulation (EC) No 726/2004, the Marketing Authorisation Holder (MAH) is conducting a program of studies as post-authorisation measures (PAMs) to further investigate the benefits and safety of Raxone[®] in the treatment of LHON patients.

One specific obligation consists of the LEROS study (SNT-IV-005): an open-label interventional Phase IV study, designed to further assess the efficacy and safety of Raxone[®] in the long-term treatment of LHON patients. According to European legislation and regulatory guidelines, LEROS qualifies as a Post Approval Efficacy Study (PAES).

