12.2 Efficacy Secondary Endpoints

Endpoint: Components of the primary endpoint: proportion of eyes with CRR of VA from BL at Month 12 compared to matching external NH control group

Analysis method: This endpoint will be analysed with methods similar as for analysing the primary endpoint as defined in section The criteria of inclusion/exclusion for the pre-planned indirect comparison of the primary endpoint against an external natural history control group, where it is only considered who are carriers of only one of the three major LHON mtDNA (G11778A, G3460A or T14484C). Due this criterion, efficacy analysis where there is an indirect comparison to the external natural history control group, will be based on the mITT population.

Primary endpoint 12.1.

Endpoint: Components of the primary endpoint: proportion of eyes in which BL VA better than 1.0 logMAR was maintained at Month 12 compared to matching external NH control group

Analysis method: This endpoint will be analysed with methods similar as for analysing the primary endpoint as defined in section The criteria of inclusion/exclusion for the pre-planned indirect comparison of the primary endpoint against an external natural history control group, where it is only considered who are carriers of only one of the three major LHON mtDNA (G11778A, G3460A or T14484C). Due this criterion, efficacy analysis where there is an indirect comparison to the external natural history control group, will be based on the mITT population.

Primary endpoint 12.1.

Endpoint: Proportion of eyes in patients treated with Raxone[®]>1 year after the onset of symptoms with CRR of VA from BL or in which BL VA better than 1.0 logMAR was maintained at Month 12 compared to external NH control group

Analysis method: This endpoint will be analysed with methods similar as for analysing the primary endpoint as defined in section The criteria of inclusion/exclusion for the pre-planned indirect comparison of the primary endpoint against an external natural history control group, where it is only considered who are carriers of only one of the three major LHON mtDNA (G11778A, G3460A or T14484C).

Study: SNT-IV-005

Due this criterion, efficacy analysis where there is an indirect comparison to the external natural history control group, will be based on the mITT population.

Primary endpoint 12.1.

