19.2 Table shell structure

Table 19-1 - Table shell for the comparison between LEROS and NH control group

Table Description	LEROS matched ITT	NH matched
Categorical variable, N	xx	xx
Category 1 n (%)	xx (xx.x%)	xx (xx.x%)
Category 2 n (%)	xx (xx.x%)	xx (xx.x%)
	xx (xx.x%)	xx (xx.x%)
Continuos variable, N	xx	xx
mean (SD ; SE)	xx.xx (xx.xx ; xx.xx)	xx.xx (xx.xx ; xx.xx)
median (Q ₁ – Q ₃)	xx.xx (xx.xx – xx.xx)	xx.xx (xx.xx – xx.xx)
min-max	xx.xx - xx.xx	xx.xx – xx.xx

Table 19-2 - Table shell for LEROS ITT population

Table Description	2 nd eye onset ≤ 1 year	2 nd eye onset > 1 year	LEROS ITT
Categorical variable, N	xx	xx	xx
Category 1 n (%)	xx (xx.x%)	xx (xx.x%)	xx (xx.x%)
Category 2 n (%)	xx (xx.x%)	xx (xx.x%)	xx (xx.x%)
	xx (xx.x%)	xx (xx.x%)	xx (xx.x%)
Continuos variable, N	xx	xx	xx
mean (SD ; SE)	xx.xx (xx.xx ; xx.xx)	xx.xx (xx.xx ; xx.xx)	xx.xx (xx.xx ; xx.xx)
median (Q₁ – Q₃)	xx.xx (xx.xx – xx.xx)	xx.xx (xx.xx – xx.xx)	xx.xx (xx.xx – xx.xx)
min-max	xx.xx - xx.xx	xx.xx – xx.xx	xx.xx – xx.xx

Table 19-3 - Table shell for primary LHON mtDNA mutations subgroup analysis

Table Description	G11778A	G3460A	T14484C	Other Mutation
Categorical variable, N	xx	XX	xx	xx
Category 1 n (%)	xx (xx.x%)	xx (xx.x%)	xx (xx.x%)	xx (xx.x%)
Category 2 n (%)	xx (xx.x%)	xx (xx.x%)	xx (xx.x%)	xx (xx.x%)
•••	xx (xx.x%)	xx (xx.x%)	xx (xx.x%)	xx (xx.x%)
Continuos variable, N	xx	xx	xx	xx
mean (SD; SE)	xx.xx (xx.xx ; xx.xx)			
median $(Q_1 - Q_3)$	xx.xx (xx.xx – xx.xx)	xx.xx (xx.xx – xx.xx)	xx.xx (xx.xx – xx.xx)	xx.xx (xx.xx – xx.xx
min-max	xx.xx - xx.xx	xx.xx – xx.xx	xx.xx – xx.xx	xx.xx – xx.xx

Table 19-4 - Table shell for age at baseline subgroup analysis

Table Description	< 18 years	≥ 18 and < 35 years	≥ 35 years
Categorical variable, N	xx	xx	xx
Category 1 n (%)	xx (xx.x%)	xx (xx.x%)	xx (xx.x%)
Category 2 n (%)	xx (xx.x%)	xx (xx.x%)	xx (xx.x%)
•••	xx (xx.x%)	xx (xx.x%)	xx (xx.x%)
Continuous variable, N	xx	xx	xx
mean (SD; SE)	xx.xx (xx.xx ; xx.xx)	xx.xx (xx.xx ; xx.xx)	xx.xx (xx.xx ; xx.xx)
median (Q ₁ – Q ₃)	xx.xx (xx.xx – xx.xx)	xx.xx (xx.xx – xx.xx)	xx.xx (xx.xx – xx.xx)
min-max	xx.xx – xx.xx	xx.xx - xx.xx	xx.xx – xx.xx

Table 19-5 - Table shell for Blindness Category of Best VA at BL subgroup analysis

Table Description	Off-chart	Legally blind	Non-legally blind
Categorical variable, N	xx	xx	xx
Category 1 n (%)	xx (xx.x%)	xx (xx.x%)	xx (xx.x%)
Category 2 n (%)	xx (xx.x%)	xx (xx.x%)	xx (xx.x%)
•••	xx (xx.x%)	xx (xx.x%)	xx (xx.x%)
Continuos variable, N	xx	xx	хх

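### SAP 12.2 gives no analysis for the by-mutation comparison with natural history that SAP 4.2 lists for two secondary endpoints; the only by-mutation analyses are in treated patients

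*SAP*

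**What the plan says.** SAP 4.2 defines two NH-controlled secondary endpoints with a split by mutation. For eyes of patients treated more than 1 year after onset, assessed at Month 12, the wording is "compared to external NH control group, in all patients and classified by mutation". For eyes and patients treated within 1 year, assessed at Months 6, 18 and 24, it is "compared to matching external NH control group, in all patients and classified by mutation". Protocol 2.2.2 agrees; its entry for the first endpoint reads "compared to external natural history control group, in all patients and classified by mutation", and protocol 9.2.2 repeats both.

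Protocol 1.2 gives the reason. It says that earlier data show mutation to be prognostic of clinically relevant recovery (CRR), and it makes it a secondary objective to provide information "on the influence of the mutation harboured on CRR rate compared to spontaneous CRR (sCRR) untreated control patients". Protocol 9.4.2 adds a minimum subgroup commitment: each of the three primary mutations analysed on its own.

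In SAP 12.2 the first endpoint ends at "was maintained at Month 12 compared to external NH control group", with nothing about mutation. The second is shortened in the same way. Both are sent to the method of SAP 12.1, a logistic model with main effects for treatment, gender and mutation. On subgroups, including mutation, SAP 9.3 says: "Subgroup analyses will be performed in LEROS ITT population". SAP 14 declares no deviations from the protocol version it cites.

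**The concern.** Two listed endpoints have a by-mutation component for which the analysis sections give no model, dataset split or output. The SAP takes precedence over the protocol where they differ, so the subgroup line in protocol 9.4.2 does not clearly fill the gap.

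The control group matters here because recovery without treatment depends partly on the mutation (protocol 1.1). A by-mutation table in treated patients alone shows prognosis and drug effect together and cannot separate them. The protocol's stated interest is recovery by mutation set against spontaneous recovery. If the method is left open, someone will have to choose it after the open-label data are available, which a SAP is meant to prevent.

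**Working it through.** **1. Tracing the by-mutation NH comparison**

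| Place | Compared with NH? | By mutation? |
|---|---|---|
| Protocol 2.2.2 and 9.2.2, SAP 4.2 (two endpoints) | Yes | Yes |
| SAP 12.2 (same two endpoints) | Yes | No |
| SAP 12.1 model | Yes | Main effect only |
| SAP 9.3, applied in sections 11 and 12.3 | No, LEROS ITT | Yes |

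No row for an analysis has both.

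**2. What the 12.1 model can deliver**

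The model is logit(p) = a + b·treatment + mutation effect + gender effect. The treatment odds ratio is exp(b), the same for every mutation. A mutation-specific value needs an interaction: exp(b + g_m) for mutation m.

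**3. What treated-only rates can show (hypothetical rates)**

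The documents give no recovery rates by mutation, so the spontaneous rates here are assumptions. The planning rates of 40% and 22% (SAP 6) imply an odds ratio of (0.40/0.60)/(0.22/0.78) = 2.36. Take two mutations with spontaneous rates of 10% and 50%:
- No drug effect (OR 1): treated rates are 10% and 50%.
- OR 2.36 in both: treated odds are 0.111 × 2.36 = 0.263 and 1 × 2.36 = 2.36, so treated rates are 21% and 70%.

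A steep gradient by mutation appears in both cases, so the treated-only table cannot tell them apart. The ranking can also reverse. With 50% treated against 45% spontaneous, OR = 1/(0.45/0.55) = 1.22. With 30% against 15%, OR = (0.30/0.70)/(0.15/0.85) = 2.43. The treated rates favour the first mutation; the controlled comparison favours the second.

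**4. Precision of the restored comparison**

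First, the plan's own figure. SAP 6 asks for 110 LEROS eyes for 90% power, 40% against 22%, and mentions 175 NH eyes. With two-sided alpha 0.05, pooled variance under the null and independent eyes:
- Pooled rate = (44 + 38.5)/285 = 0.2895.
- Null SE = √[0.2895 × 0.7105 × (1/110 + 1/175)] = 0.0552; alternative SE = √[0.24/110 + 0.1716/175] = 0.0562.
- Power = Φ[(0.18 − 1.96 × 0.0552)/0.0562] = Φ(1.28) = 0.90 (0.899 unrounded; 111 eyes pass 0.90).

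The figure reproduces, but for all mutations pooled. No by-mutation comparison is sized.

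Now suppose a mutation has the same share s in both groups, with 40% against 22% in it. The documents give no split, so s is an assumption. These counts belong to the ≤1 year Month 12 comparison and stand in for the others.

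| Share | LEROS / NH eyes | Power | Power, assumed design effect 1.5 |
|---|---|---|---|
| 10% | 11 / 17.5 | 0.18 | 0.14 |
| 20% | 22 / 35 | 0.31 | 0.23 |
| 30% | 33 / 52.5 | 0.43 | 0.31 |
| 60% | 66 / 105 | 0.71 | 0.54 |
| 80% | 88 / 140 | 0.83 | 0.66 |

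Approximate intervals use SE(log OR) = √[1/(n₁ × 0.24) + 1/(n₂ × 0.1716)], with independent eyes. At 10%: √(0.379 + 0.333) = 0.844, so 2.36 with 95% CI 0.45 to 12.4. At 60%: 0.344, so 1.20 to 4.64.

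**The case against.** The strongest reply is that nothing has been removed. Both endpoints are still in SAP 4.2 with their mutation classification, and SAP 8.2 and 8.4 say that the ITT and NH sets will be used for the section 4 endpoints. SAP 9.3 also covers age and baseline acuity and nowhere claims to replace the NH comparison. This stands. A reader might infer that the comparison was dropped or swapped for treated-only subgroups; the documents support only that it is listed and not given an analysis.

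A reader might also infer that the mutation objective cannot be met. As worded in SAP 3.2 and protocol 2.1.2, that objective concerns treated patients, and LEROS-only subgroups answer its literal text. The need for a control comes from the endpoints and from protocol 1.2.

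The table shells are weak evidence. "Table 19-3 - Table shell for primary LHON mtDNA mutations subgroup analysis" has no NH column, but all shells in SAP 19.2 are generic, and none holds an odds ratio even for the primary endpoint.

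It is also fair that mutation is in every NH logistic model, which protects the overall odds ratio from imbalance in mutation. It does not produce an odds ratio for each mutation. Finally, strata will be small. That argues for intervals and modest claims, or for declaring the omission, but not for leaving a listed endpoint without a method.

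**Conclusion.** The point holds as an inconsistency between SAP 4.2 and SAP 12.2. Followed as written, SAP 9.3, 12.1 and 12.2 yield no mutation-specific Raxone-versus-NH estimate for either endpoint, and SAP 14 does not declare this. The reach is limited to secondary and subgroup results. The primary endpoint carries no mutation classification in SAP 4.2; its by-mutation analysis rests on protocol 9.4.2 alone, and the primary conclusion is unaffected.

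A reader might go further and conclude that treated-only tables mainly reproduce natural prognosis, or will rank the mutations wrongly. The documents do not support that. They say that mutation is prognostic, not how strongly relative to the drug. The rates in step 3 are hypothetical and show that reversal is possible, not that it is likely. The precision figures rest on assumed mutation shares, planning rates common to all strata and, except in the design-effect column, independent eyes. The conclusion about the missing analysis rests on none of these.

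This should be corrected because it is cheap, and the results should be read as estimates.

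**What to change.** - **Restore the endpoint.** In SAP 12.2, put the mutation classification back for the two endpoints. Under protocol 9.4.2, add it as a subgroup analysis of the primary endpoint.
- **Model.** Add a treatment-by-mutation term to the 12.1 model on the mITT/NH matched sets. Report the Raxone-versus-NH odds ratio with 95% CI for G11778A, G3460A and T14484C, with patients, eyes and responders per arm beside each.
- **Dependence.** Use standard errors that allow for two eyes per patient and, beyond 1 year, for one NH eye contributing a record in several time-since-onset bins (SAP 8.5.2). Plain logistic intervals ignore both.
- **Sparse data.** Name one method for all strata, for example Firth penalised likelihood, and not only when a cell is empty. A patient-level bootstrap of the penalised fit would meet this and the previous item together.
- **Presentation.** Use a separate mITT/NH-matched table by mutation. Keep Table 19-3 as LEROS-only description: it uses ITT patients classified by the most recently affected eye, while 12.1 uses mITT eyes classified by their own onset, so NH columns there would mix populations. Show time since onset by arm within mutation, because SAP 8.5.1 matches to one overall average.
- **Label.** State that these are estimates, not powered tests.

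If the sponsor prefers not to do this, SAP 14 should declare the omission. The cost is one model term, a clustered interval method and one table on existing data. The downside is wide intervals for the rarer mutations.

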10.1 LEROS

The disposition of patients in LEROS will be summarized as presented in Figure 10.1.1 workflow diagram and Table 10-1.

Figure 10.1.1- LEROS subject disposition

[figure not shown]

Table 10-1 LEROS duration of follow-up

	1 day	≥ 3 months	≥ 6 months	≥ 9 months	≥ 12 months	≥ 18 months	≥ 24 months
N	хх	xx	xx	Xx	Xx	xx	Xx
%	xx.x	xx.x	xx.x	xx.x	xx.x	хх.х	xx.x

Patients center disposition will be tabulated presenting the number and percentage of patients enrolled, patients in Safety population and patients in ITT population, in total and by year after the onset of symptoms. Information will be order by center identification and shown as presented in Table 10-2.

Table 10-2 LEROS patients by center

F	Patients by center	Onset ≤ 1 year ¹	Onset > 1 year ¹	Total of patients
	Patients Enrolled	xx (xx.x%)	xx (xx.x%)	xx (xx.x%)
Center	Safety population	xx (xx.x%)	xx (xx.x%)	xx (xx.x%)
	ITT population	xx (xx.x%)	xx (xx.x%)	xx (xx.x%)

¹ Time since symptoms onset of most recent affected eye at baseline.

Listings: For enrolled patients it will be provided the following listings order by center and patient identification:

- date of inform consent, date of baseline visit, date of last recorded study visit, reason for end of study
 completion/discontinuation (if applicable, reason for study discontinuation), and date of symptoms onset of
 most recent affected eye at baseline;
- analysis population: Safety population, ITT (Intent-To-Treat population), modified ITT population;
- patients who did not meet the inclusion/exclusion criteria or confirmation of either G11778A, G3460A or T14484C was not present at baseline.

10.2 Natural History

The disposition of patients in Natural History (CRS-1 and CRS-2 patients) will be summarized as presented in Figure 10.2.1 workflow diagram and Table 10-3.

SNT-IV-005 Statistical Analysis Plan

Confidential

Figure 10.2.1- Natural History subject disposition

[figure not shown]

Table 10-3 Natural History duration of follow-up

	1 day	≥ 3 months	≥ 6 months	≥ 9 months	≥ 12 months	≥ 18 months	≥ 24 months	≥ 60 months
N	xx	хх	хх	хх	хх	xx	xx	xx
%	XX.X	xx.x	XX.X	XX.X	xx.x	XX.X	xx.x	xx.x

Patients center disposition will be tabulated presenting the number and percentage of patients per Case Report Survey. Information will be order by center identification as presented Table 10-4.

Table 10-4 Natural History patients by center

Patients by center	CRS-1	CRS-2	Total of patients
Center 1	xx (xx.x%)	xx (xx.x%)	xx (xx.x%)
Center 2	xx (xx.x%)	xx (xx.x%)	xx (xx.x%)
	xx (xx.x%)	xx (xx.x%)	xx (xx.x%)

SNT-IV-005 Statistical Analysis Plan

Confidential

V1.0 07 June 2021

₹00

Listings: It will be provided a list with date of informed consent, date of first recorded visit and date of last recorded visit, order by report survey, center and patient identification.

11 Data Collection and Analysis

